reduction (75%) in recurrent VTE as low-intensity rivaroxaban (10 mg daily) compared with low-dose aspirin (2). The 75% relative risk reduction was reported specifically for recurrent VTE and in the provoked VTE patient population, comparing rivaroxaban 10 mg daily versus low-dose aspirin. This relative risk reduction specifically pertains to our primary study outcome and our exact patient population and comes from a robust randomized controlled trial analysis. If anything, the reduction in the proposed study should be even greater since we propose a placebo-control instead of active (aspirin) control and we will be following our patients for 12 months, instead of allowing shorter follow-up as was reported in EINSTEIN CHOICE. Accordingly, assuming an estimated incidence in the placebo group of 6% at 12 months and a decrease in the primary outcome of 75% with apixaban 2.5 mg twice daily as compared with placebo, we calculated that we would need to enroll 279 patients in each group for the study to have 80% power to show the superiority of low-intensity apixaban over placebo, at a two-sided alpha level of 0.05. To account for patients who may be lost to follow-up or withdraw from the study, we will recruit 300 in each arm and 600 total.

EINSTEIN-CHOICE enrolled patients after a required 6 to 12 months of anticoagulant therapy. Our study requires that patients complete at least 3 months of anticoagulant therapy in accordance with current and widely-accepted evidence-based clinical practice guidelines (Eur Heart J. 2020; 41: 543–603, Chest. 2016;149:315-352, and Circulation. 2011;123:1788–1830). Data from the PADIS-PE study showed that the rate of VTE recurrence is higher closer in temporal proximity to the initial event, such that the recurrence rate is higher at 3-6 months after diagnosis than it is at 6-12 months (Couturaud F, et al. Six Months vs Extended Oral Anticoagulation After a First Episode of Pulmonary Embolism. JAMA. 2015;314(1):31-40). Accordingly, the anticipated event rate should be higher in our study than EINSTEIN-CHOICE and the resultant observed relative risk reduction is likely to be higher.

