Baseline characteristics will be summarized by group. Any imbalances between the treatment groups for any demographic or baseline characteristic will be assessed based on clinical relevance in reviewing the summaries. For any differences deemed clinically relevant to the efficacy comparisons, exploratory analyses that include the imbalanced factor as a categorized covariate will be performed.

To account for the effect of baseline low-dose aspirin use in the study population on the rate of recurrent VTE after an initial provoked event, we will perform a pre-specified stratified efficacy analysis of patients receiving low-dose apixaban or placebo with low-dose aspirin compared with patients just receiving low-dose apixaban or placebo. We will calculate stratum-specific risk ratios (RR). Comparing the “crude” (overall or unadjusted) and stratum-specific risk ratios will enable us to determine whether aspirin modifies the effect of low-dose apixaban and to what extent. If the stratum-specific risk ratio is similar to the crude risk ratio, then there is minimal impact of low-dose aspirin. However, if the stratum-specific risk ratio differs from the unadjusted estimate by 10% or more, then low-dose aspirin modifies the effect of low-dose apixaban. We will conduct a similar analysis for the safety outcome of major bleeding.

We will also pre-specify subgroup analyses focused on the safety and efficacy of major populations of interest, in particular, elderly patients (age \geq 65 years), women, and those with persistent provoking factors of immobility, obesity, heart failure, chronic lung disease, chronic kidney disease, hemodialysis, chronic inflammatory/autoimmune disorder, and atherosclerotic cardiovascular disease.

Means, medians, and frequency distributions will be calculated for continuous variables. Number and percentages will be reported for binary and categorical variables. Differences between subgroups of interest will be examined using the chi-square or Fisher's exact test for binary and categorical variables and t-test or Wilcoxon Rank Sum for continuous variables (if the subgroups are of sufficient size for statistical comparison).

Safety outcome analyses will be performed among patients who received one or more doses of a study drug (Safety Population). All p-values reported will be two-sided. A p-value < 0.05 will be considered significant. All analyses will be performed using SAS software.

Interim Analysis

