4.1.2 Secondary Efficacy Outcomes

Secondary efficacy outcomes include the time to first occurrence of a composite of death due to cardiovascular causes, nonfatal myocardial infarction (MI), stroke or systemic embolism, chronic limb-threatening ischemia (CLTI), or coronary or peripheral ischemia requiring revascularization (major adverse cardiovascular events, including major adverse limb events) within 12 months, and the individual components of this outcome. An additional composite outcome will include all the components of the above composite of major adverse cardiovascular events as well as symptomatic VTE. A composite thrombotic outcome will be analyzed and will include symptomatic VTE, fatal or nonfatal myocardial infarction (MI), stroke/TIA or systemic embolism. The secondary efficacy outcomes will be independently adjudicated by a CEC blinded to assigned treatments. Non-cardiovascular death will be considered a competing risk.

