4.2.2 Secondary Safety Outcome

The time to first clinically relevant non-major bleeding within 12 months will be evaluated and is defined per the ISTH as overt bleeding that does not meet the criteria for major bleeding but that is associated with the need for medical intervention, unscheduled contact with a physician, interruption or discontinuation of the study drug, or discomfort or impairment of activities of daily living 2. Like the primary safety outcome, this outcome will be assessed by the CEC, blinded to assigned treatments. All-cause death will be considered a competing risk for this outcome. We will also assess a composite outcome of major bleeding and clinically-relevant nonmajor bleeding. Non-hemorrhagic death will be considered a competing risk for these outcomes.

For all the outcomes, the last time contact date will be used for determining censoring.

5. Details of Randomization and Blinding

Subjects who are 18 years of age or older with provoked DVT and/or PE, have completed at least 3 months of therapeutic anticoagulation, have a low risk of bleeding, and have at least one enduring risk factor will be randomly assigned by computer in a 1:1 ratio to receive apixaban 2.5 mg orally twice daily or oral placebo for extended secondary prevention of VTE for a duration of 12 months.

This study will be conducted in a blinded fashion. To maintain blinding of study treatment, the active study drug and placebo will be matched for color, size and box. Subjects, investigators, members of any of the administrative and adjudicating committees, and the Sponsor's staff conducting the study, will not have access to individual subject treatment assignments.

An independent Safety Monitor has been selected for this study. The Safety Monitor is an expert in VTE and is distinct from the DMSB and Study Staff and will be available throughout the study to assess patient safety issues that may arise, objectively. The Safety Monitor will have the ability to break the blind of a study patient as the need arises (immediately, in real-time). If the Safety Monitor is unavailable because of travel, one of the Physician Study Investigators will serve as back-up.

6. Statistical Plan

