6.1 Power Calculation

Our power calculation accommodates efficacy outcomes. This is an implementation of the power calculation method described in Section 14.12 (page 807) of Rosner (2006). The equation of power calculation based on 1:1 randomization is expressed as below:

$$Power = \Phi \left(\frac{\sqrt{m}|\lambda - 1|}{\lambda + 1} - Z_{1-\frac{\alpha}{2}} \right),$$

where m is the expected total number of events over both groups, n is the total sample size, p_E and p_c are the probabilities of event in treatment group and placebo group over the maximum time of the study, λ is postulated hazard ratios for the treatment over placebo.

We postulated the following anticipated parameters for the power calculation: a) by the end of follow up, the event rate of the placebo arm is 6% and there is 75% reduction rate with active treatment (low-intensity apixaban), i.e., the event rate of the placebo arm is 1.5%; b) the postulated hazard ratios for the treatment over placebo by 1-year follow-up ranges from 0.2-0.24. These anticipated parameters are based on previous studies ^{3,4}. In Figure 1, we provide the power analysis given certain sample size. The power under the significance of 0.05 is given for the total sample with 1:1 randomization ranging from 500-700. To achieve sufficient sample sizes needed for reach the power of 80%, we conservatively choose 600 patients to ensure the enough power.

[figure not shown]

Figure 1. The power calculation given the postulated hazard ratios and with 1:1 randomization. The red curve indicates the power of 80%.

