6.4 Survival Analysis

6.4.1 Principal Analysis

We first provide analysis without adjustment of baseline demographics. For both the primary and secondary efficacy outcomes and principal and secondary safety outcomes, we use the Kaplan-Meier curve to estimate the survival functions of each group. If there is a presence of competing risks, cumulative incidence functions (CIFs) will be used to estimate the survival function⁷. The two-side log-rank test is used to measure if the apixaban 2.5 mg twice a day has a better survival chance than placebo (i.e., better chance of meeting the primary outcome). If there is a presence of competing risk, the log-rank based on cause-specific hazards⁸ will be used. The corresponding hazard ratio of treatment effect and its confidence interval will be reported.

While our analysis is based on randomization, we also provide confirmatory analyses with the adjustment of baseline demographics and clinical comorbidities since it may capture any potential variations to make the statistical analysis more powerful. We use Cox regression to assess both the primary and secondary efficacy outcomes, while with adjustment of baseline demographics and clinical comorbidities. No interaction effects will be added. If there are competing risks, a cause-specific hazard model⁷ will be used. The hazard ratio for being treatment with the apixaban 2.5 mg twice a day will be used to test the treatment effect. The hazard ratio of other baseline demographics will be reported as supplementary information.

If the trial has a good randomization, we expect that the hazard ratio of treatment in analysis with the adjustment of baseline demographics and its p-value implies the same conclusion as in analysis without adjustment of baseline demographics. However, if they are not consistent in

clinical interpretation, i.e., a) the interpretation directions are different; b) p-values indicate different conclusion of significance, we will use the hazard ratio of treatment in analysis with the adjustment of baseline demographics as the main results to report, and the results of unadjusted one is treated as supplementary materials.

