6.4.2 Subgroup Analysis

The study will conduct subgroup analyses based on certain predetermined factors such as whether the patient has PE versus non-PE, age (65 years or older versus younger), sex (male versus female), chronic kidney disease (defined as presence or absence of eGFR<60 mL/min/1.72m²), atherosclerotic cardiovascular disease (present versus absent), baseline low-dose aspirin use (present versus absent), the number of provoking risk factors (2 or more versus less than 2), provoking factor of travel, and baseline aspirin use. The survival analysis within each subgroup will be repeated using the main cohort and tested in confirmatory cohorts, as needed. The p-value of the additive interaction effect between treatment and subgroup will be reported.

In case the subgroup analysis of baseline aspirin use indicates a relevant modification effect (the p-value for the additive interaction effect <0.05), the study will repeat the primary analysis by reporting the treatment effect of apixaban vs placebo with the adjustments for a) the use of aspirin and b) the interaction term.

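### The SAP widens two secondary outcomes to ten and reports eight subgroup interaction p-values with no testing order, adjustment or exploratory label, while the only general significance rule is the protocol's p < 0.05.

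*Combined protocol and SAP*

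**What the plan says.** The protocol has one secondary efficacy outcome (the cardiovascular and limb composite, MACE/MALE below) and one secondary safety outcome (clinically relevant non-major, CRNM, bleeding).

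The SAP has more. Section 4.1.2 keeps the composite and adds its individual components, a broader composite ("An additional composite outcome will include all the components of the above composite of major adverse cardiovascular events as well as symptomatic VTE") and a thrombotic composite that also contains symptomatic VTE. Section 4.2.2 keeps CRNM bleeding and adds another outcome: "We will also assess a composite outcome of major bleeding and clinically-relevant nonmajor bleeding".

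SAP 6.4.1 opens with "For both the primary and secondary efficacy outcomes and principal and secondary safety outcomes, we use the Kaplan-Meier curve"; that sentence concerns estimation of survival functions. The two-sided log-rank test follows, with a parenthesis that mentions only the primary outcome. The next paragraph is explicit: Cox regression is applied to primary and secondary efficacy outcomes, and the treatment hazard ratio is used for testing. The section then compares adjusted with unadjusted results partly by whether they agree on significance. If they disagree, the adjusted result becomes the main one.

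SAP 6.4.2 lists the subgroup factors and states: "The p-value of the additive interaction effect between treatment and subgroup will be reported".

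The SAP gives no threshold for the secondary outcomes. In the SAP, 0.05 appears in the power section ("The power under the significance of 0.05 is given for the total sample with 1:1 randomization ranging from 500-700") and for the aspirin interaction. The general rule is in the final protocol, Statistical Methods, Statistical Analysis Plan: "All p-values reported will be two-sided", followed by "A p-value < 0.05 will be considered significant".

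**The concern.** Read together, the two documents allow any secondary outcome to be called significant at 0.05, in any order and whether or not the primary succeeds. Three provisions might have limited this, and none does:

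- SAP Table 6.2.1 gives a p-value in only one analysis set per outcome, but covers only the two primary outcomes.
- The protocol's Hochberg sentence concerns only the primary claim.
- The protocol uses the word exploratory only for models that adjust for baseline imbalance.

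At stake is what the trial may claim beyond its primary result. A single component, an added composite or a subgroup could be presented as a finding when it is chance. The two VTE-containing composites raise a different problem, one of interpretation: they can reach significance on VTE alone and be cited as cardiovascular benefit.

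**Working it through.** **1. The plan's own figure.** The protocol sizes the trial "assuming an estimated incidence in the placebo group of 6% at 12 months and a decrease in the primary outcome of 75% with apixaban", that is 6% vs 1.5%, at two-sided alpha 0.05 and 80% power. With pooled variance and mean proportion 0.0375:

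n = [1.96·√(2·0.0375·0.9625) + 0.8416·√(0.06·0.94 + 0.015·0.985)]² / 0.045² = (0.5266 + 0.2245)² / 0.002025 ≈ 278.6

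This gives 279 per group with power 0.8005, as the protocol states. Neither document gives an error rate for the secondary outcomes or subgroups.

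**2. Counts.**

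| Source | Outcomes | Number |
|---|---|---|
| SAP 4.1.2 | MACE/MALE composite | 1 |
| SAP 4.1.2 | its components, as listed | 5 |
| SAP 4.1.2 | MACE plus VTE | 1 |
| SAP 4.1.2 | thrombotic composite | 1 |
| SAP 4.2.2 | CRNM bleeding | 1 |
| SAP 4.2.2 | major or CRNM bleeding | 1 |
| Total | | 10 |

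SAP 6.4.2 lists nine subgroup factors with aspirin twice, so eight are distinct.

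**3. Chance of at least one p < 0.05 under no effect, by formula.** Independent tests: 1 − 0.95^k, which is 40.1% for k = 10 and 33.7% for k = 8. For two-sided z-tests with common correlation ρ and c = 1.96:

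1 − ∫ φ(u)·[Φ((c − √ρ·u)/√(1 − ρ)) − Φ((−c − √ρ·u)/√(1 − ρ))]^k du

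| ρ | 10 outcomes | 8 interactions |
|---|---|---|
| 0 | 40.1% | 33.7% |
| 0.5 | 28.7% | 25.0% |
| 0.8 | 17.3% | 15.7% |
| 0.9 | 12.8% | 11.9% |

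The documents give no correlation, so ρ is an assumption. Counting only chance results that favor apixaban, the figure at ρ = 0.5 is about 14% for ten outcomes.

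**4. The same chance by simulation of the overlapping outcomes.** Log-rank tests, 300 per arm, 12 months, independent event types, VTE 6% in both arms. The other rates are assumptions, because the documents give none.

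- Component rates from 0.2-1% (low) to 2-5% (high), CRNM bleeding 3-10%, major bleeding 0.5-2%, no loss: 25.8% (low), 31.6% (middle), 32.4% (high). In the low scenario the rarest components reject in well under 5% of trials, which lowers the total.
- CV death 0.5%, MI 1%, stroke or systemic embolism 0.8%, limb ischemia 0.5%, revascularization 1.5%, CRNM bleeding 3%, major bleeding 0.4%, or all doubled, with 7% loss (279/300 = 93% retained): 29-33% over repeated runs. A significant secondary together with a non-significant primary occurs in 25-30%.

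Together these give about 26-33%. The adjusted Cox re-test and the rule that can promote it are not counted; they would raise the total.

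**5. VTE-containing composites.** With the second set of rates, VTE at 1.5% vs 6% and no arterial effect:

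| Composite | Doubled rates | Base rates |
|---|---|---|
| MACE plus VTE | about 34% | about 49-51% |
| Thrombotic | about 52% | about 66-68% |

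These are probabilities of p < 0.05 when a real VTE difference exists, so they are power and not error.

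**The case against.** The strongest reply is that the SAP never says these analyses are each tested against 0.05. A reader might infer that it does, but the SAP sets no threshold for the secondary outcomes or for seven of the eight subgroup factors. The rule is protocol text, written alongside a different primary test (Mantel-Haenszel). Log-rank testing of the secondary outcomes is implied, and no sentence plainly tests the two secondary bleeding outcomes. This stands as a limit on wording. It does not remove the point: Cox testing of secondary efficacy is explicit, SAP 6.4.1 judges agreement by significance, and the protocol's sentence is the only general rule available for that.

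Second, a reader might take a single figure near 29% as established, or as covering the subgroups too. Neither is supported. That value needs an assumed correlation of 0.5 or assumed event rates, and it concerns the ten outcomes only. About half of the chance results would also point to harm.

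Third, a reader might count significance of the VTE-containing composites as false positives. They are not: if apixaban prevents VTE, those composites truly differ between arms. The SAP defines their content openly and also reports the cardiovascular composite without VTE.

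Fourth, interaction p-values are only reported, and the one with a threshold (aspirin) merely triggers a repeat of the primary analysis with adjustment. This is fair, and it makes the subgroup part the weaker one.

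Finally, the primary claim is untouched. That is correct and limits the importance of the point.

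**Conclusion.** The concern holds in limited form. Ten secondary outcomes and eight distinct subgroup factors have no testing order, adjustment or exploratory label, and the only general significance rule is the protocol's 0.05. Under no effect, at least one secondary outcome would be called significant in about 26-33% of trials under the assumed event rates, or 13-40% for assumed correlations from 0.9 to 0. Every value in that range exceeds twice 5%. The eight interactions are a separate family, at about 25-34% for correlation 0.5 down to independence.

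A reader might go further and conclude that the primary efficacy error rate is inflated. The documents do not support that: there is one primary efficacy outcome, the others are labelled secondary, and Table 6.2.1 gives the primary efficacy outcome a p-value only in the ITT set. For the VTE-containing composites the issue is interpretation: a significant result should not be read as arterial benefit.

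**What to change.** In SAP 6.4.1:

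- State that the ITT primary efficacy log-rank test is the confirmatory efficacy test.
- Test the protocol's MACE/MALE composite at two-sided 0.05 only if the primary is significant.
- Report the components, the two VTE-containing composites, the secondary bleeding outcomes and the subgroups as hazard ratio or cumulative incidence with 95% CI, marked exploratory and not adjusted for multiplicity, with no significance statement.
- State beside the two VTE-containing composites that they include the primary outcome.
- State that the SAP supersedes the protocol's general p < 0.05 sentence for these analyses.
- Amend the rule that promotes the adjusted Cox result, keeping the unadjusted ITT result as the main one; otherwise the section would contradict itself.

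This extends the restraint that Table 6.2.1 already applies to the primary outcomes. It needs no patients or data, only SAP wording that also settles its precedence over the protocol sentence. The downside is that the sponsor can no longer call a single component, added composite or subgroup result significant.

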The EINSTEIN CHOICE trial recently evaluated the safety and efficacy of regimens of full- or lower-intensity anticoagulant therapy versus low-dose aspirin for secondary prevention of VTE after an initial provoked or unprovoked event (2). The EINSTEIN CHOICE Investigators randomly assigned 3396 patients with VTE to receive either once-daily rivaroxaban (at doses of 20 mg or 10 mg) or 100 mg of aspirin. Prior to enrollment in EINSTEIN CHOICE, all study patients completed 6 to 12 months of anticoagulation therapy, and their providers were in equipoise regarding the need for extended anticoagulation. Approximately 60% of patients in EINSTEIN CHOICE had suffered provoked VTE. Symptomatic recurrent VTE occurred in 17 of 1107 patients (1.5%) receiving 20 mg of rivaroxaban and in 13 of 1127 patients (1.2%) receiving 10 mg of rivaroxaban, and in 50 of 1131 patients (4.4%) receiving low-dose aspirin (hazard ratio for 20 mg of rivaroxaban vs. aspirin, 0.34; 95% confidence interval [CI], 0.20 to 0.59; hazard ratio for 10 mg of rivaroxaban vs. aspirin, 0.26; 95% CI, 0.14 to 0.47; $P<0.001$ for both comparisons). Rates of major bleeding were similar (0.5% in the group receiving 20 mg of rivaroxaban, 0.4% in the group receiving 10 mg of rivaroxaban, and 0.3% in the low-dose aspirin group) (2).

Data from 4,553 patients in EINSTEIN CHOICE and the EINSTEIN VTE Continued Treatment Study demonstrate that provoked VTE patients with persistent provoking

factors have a reduction in recurrence with extended duration anticoagulation compared with low-dose aspirin or placebo (1.5% vs. 4.9%) (2,3). Common persistent provoking factors included immobility, obesity, heart failure, and chronic inflammatory disorders, such as Crohn's Disease and rheumatoid arthritis. Despite being highly prevalent, persistent provoking factors are rarely considered when stopping anticoagulation in patients with provoked VTE who have completed the typical 3- to 6-month duration of therapy. The 2016 American College of Chest Physicians (ACCP) Guidelines on Antithrombotic Therapy for VTE do not distinguish between transient and persistent provoking risk factors and recommend limited-duration anticoagulation for provoked events (4).

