Table. 8 Harvard Catalyst Biostatistics Program Consultant Sample Size Calculation Using Lower Limit of 95% Confidence Interval of Our Observational Cohort Estimate (performed by [name] using STATA).

Anticipated Event Rate = 8.2%

. power twoproportions .082 .0205, test(chi2) n(558)
 
Estimated power for a two-sample proportions test
 
Pearson's chi-squared test
 
Ho: p2 = p1 versus Ha: p2 != p1
 
Study parameters:
 
 alpha = 0.0500
 
 N = 558
 
 N per group = 279
 
 p1 = 0.0820
 
 p2 = 0.0205
 
Estimated power: power = 0.9111
 
Required N = 279 per group

Using this more conservative sample size calculation, we would aim to enroll 300 patients in each arm for a total trial population of 600.

Statistical Analysis Plan

For this study, we will calculate:

- 1) the 12-month frequency of major and clinically relevant non-major bleeding
- 2) the 12-month frequency of symptomatic recurrent VTE

The primary efficacy objective of this trial is to determine whether apixaban 2.5 mg twice daily is superior to placebo for the primary endpoint of symptomatic, recurrent VTE after 12 months of extended therapy. The analysis will include descriptive statistics of event rates and 95% CI, and risk difference and 95% CI. The Mantel-Haenszel statistic will be used to test this hypothesis formally. Superiority over placebo will be claimed for a dose if the Hochberg adjusted p-value is ≤ 0.05 and the RR is < 1 . The analysis will be supported by Kaplan-Meier curves. The primary efficacy outcome analysis will be intention-to-treat. We will also perform an on-treatment analysis.

The primary safety objective will be to determine whether apixaban 2.5 mg twice daily results in a statistically significant difference in major bleeding at 12 months (during the treatment period) compared with placebo. Analysis of incidence of these endpoints will be based on the safety analysis set. The analysis will include descriptive statistics of event rates and 95% CI, and risk difference and 95% CI. Hypotheses will be tested using Mantel-Haenszel statistic. The analysis will be supported by Kaplan-Meier curves of the time to first adjudicated major bleeding event. All bleeding analyses will be conducted on the safety dataset.

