4.2 Safety Outcomes

4.2.1 Principal Safety Outcome

The principal safety outcome will be the time to first major bleeding within 12 months from randomization. Major bleeding is defined according to the International Society on Thrombosis and Haemostasis (ISTH) as overt bleeding that is associated with a decrease in the hemoglobin level ≥ 2 g/dL, leads to transfusion ≥ 2 units of packed red blood cells, occurs in a critical site, or contributes to death 1. The principal safety outcome will be independently adjudicated by a blinded CEC review. Non-hemorrhagic death will be considered a competing risk for this outcome.

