6.2 Cohort Definition

In this section, we define a main cohort and four confirmatory cohorts for the analysis of efficacy and safety (**Table**).

Main Cohort (ITT): we will use the intention-to-treat (ITT) cohort since it maintains the original randomization scheme ("as randomized")⁵.

Confirmatory Cohort (MITT): the modified intention-to-treat (MITT) cohort consisting of all randomized patients who took at least one dose of the assigned treatment and did not undergo post-randomization exclusion.

Confirmatory Cohort (PP-1): Additional analyses will include a per-protocol (PP) population for subjects who took 80% of the study drug (or placebo).

Confirmatory Cohort (PP-2): Additional analyses will include a per-protocol (PP) population for subjects who took 80% of the study drug (or placebo) with censoring for either ISTH major bleeding or clinically relevant nonmajor bleeding event.

Confirmatory Cohort (Safety Cohort): In this cohort, we will only consider bleeding events (major bleed or clinically relevant non-major bleed) that occurred within 96 hours of taking a dose of the study drug (or placebo). The follow-up duration will be considered until the occurrence of a bleeding event or 96 hours after taking the last dose of the study drug (or placebo), whichever comes first.

6.2.1 Table. Analysis cohorts.

Analysis Set	Definition	Primary Efficacy-12-month recurrent symptomatic VTE	Primary Safety-12-month ISTH major bleeding
ITT	All randomized	Number of events Proportion Cumulative incidence Hazard ratio 95% confidence interval P-value	Number of events Proportion Cumulative incidence Hazard ratio 95% confidence interval
mITT	All randomized who took at least one dose of assigned treatment (apixaban or placebo) and did not undergo post-randomization exclusion	Number of events Proportion Cumulative incidence Hazard ratio 95% confidence interval	Number of events Proportion Cumulative incidence Hazard ratio 95% confidence interval
Per protocol without censoring for bleeding events	Subjects who took 80% of assigned treatment doses (apixaban or placebo)	Number of events Proportion Cumulative incidence Hazard ratio 95% confidence interval	Number of events Proportion Cumulative incidence Hazard ratio 95% confidence interval

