Per protocol with censoring for bleeding events	Subjects who took 80% of assigned treatment doses (apixaban or placebo) with censoring for either ISTH major bleeding or clinically relevant nonmajor bleeding event	Number of events Proportion Cumulative incidence Hazard ratio 95% confidence interval	Number of events Proportion Cumulative incidence Hazard ratio 95% confidence interval
Safety set	Subjects who took at least one dose of the study drug (or placebo) until	Number of events Proportion Cumulative incidence Hazard ratio	Number of events Proportion Cumulative incidence Hazard ratio

	96 hours after the administration of the last dose of the study drug.	95% confidence interval	95% confidence interval P-value
--	---	-------------------------	---

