6.5 Back-Up Methods if Proportional Hazard Assumption is Violated

The Cox regression relies on the assumption of proportional hazards over time. The hazard proportionality test⁹ is used to check the assumption. If the assumption of proportional hazard is violated. We will use the following backup methods. The log-rank test will be replaced by Kaplan–Meier curve-based tests (including weighted Kaplan–Meier and restricted mean survival time)¹⁰. Survival analysis based on restricted mean survival time will be implemented and restricted mean time lost (RMTL) ratios will replace the hazard ratio for reporting.

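### The SAP drops the protocol's risk difference for major bleeding, leaving a hazard ratio that may often not be estimable and no rule for an arm with zero events

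*Combined protocol and SAP*

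**What the plan says.** SAP 4.2.1 defines the outcome as a time to event: "The principal safety outcome will be the time to first major bleeding within 12 months from randomization". SAP 6.4.1 sets one analysis for efficacy and safety: "For both the primary and secondary efficacy outcomes and principal and secondary safety outcomes, we use the Kaplan-Meier curve", with cumulative incidence functions where there are competing risks, a two-sided log-rank test, and then: "The corresponding hazard ratio of treatment effect and its confidence interval will be reported".

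SAP Table 6.2.1 gives the outputs for major bleeding in each of the five analysis sets: "Number of events Proportion Cumulative incidence Hazard ratio 95% confidence interval". The safety set adds a P-value. Counts, proportions and cumulative incidences describe each arm; no difference or ratio of them is listed.

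SAP 6.5 offers a substitute only if proportional hazards fails: "restricted mean time lost (RMTL) ratios will replace the hazard ratio for reporting".

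The protocol (Statistical Methods, Statistical Analysis Plan) says of the major-bleeding comparison: "The analysis will include descriptive statistics of event rates and 95% CI, and risk difference and 95% CI", with a Mantel-Haenszel test on the safety set. The SAP neither repeats nor withdraws this.

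On expected rates, the protocol's Introduction and Background reports from a rivaroxaban versus aspirin extended-treatment trial: "0.4% in the group receiving 10 mg of rivaroxaban, and 0.3% in the low-dose aspirin group".

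**The concern.** Major bleeding is the primary safety outcome and the subject of Specific Aim 2. The protocol's hypothesis is that the two arms will have similar rates, so the useful result is an interval showing how large an excess can be excluded. A P-value from very few events cannot do that.

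The cited rates imply about one major bleed per arm. With no bleeds on apixaban the estimated hazard ratio is zero; with none on placebo it is infinite; with none in either arm it cannot be computed. A risk difference can be estimated in all three cases. Because the SAP omits it and is silent on zero events, the analyst would have to choose a substitute after seeing the data, or fall back on a protocol passage that the SAP appears to replace.

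**Working it through.** **Plan's own figure.** The documents state no power, expected event count or precision for major bleeding, so there is none to reproduce. The efficacy figure does reproduce: 279 per group, 6% versus 1.5%, two-sided 0.05, gives power 0.8005.

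**Inputs.**
- 300 per arm, 1:1 (protocol, Sample Size Calculation; SAP 3.1).
- 12-month major-bleeding risk of 0.4% for apixaban and 0.3% for placebo. These are proxies: the rivaroxaban 10 mg and aspirin arms of the cited trial.

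**Expected events.** 300 × 0.004 = 1.2 and 300 × 0.003 = 0.9.

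**Chance of an empty arm.** P(no events) = (1 − p)^300.
- Apixaban: a = 0.996^300 = 0.3005.
- Placebo: c = 0.997^300 = 0.4060.

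| Result | Formula | Probability |
|---|---|---|
| Hazard ratio zero | a(1 − c) | 17.8% |
| Hazard ratio infinite | c(1 − a) | 28.4% |
| Undefined, both arms empty | ac | 12.2% |
| Any of these | a + c − ac | 58.4% |

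One million simulated trials also gave 58.4%.

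**Sensitivity.**

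| Per arm | Apixaban / placebo risk | At least one arm empty |
|---|---|---|
| 279 | 0.4% / 0.3% | 61.8% |
| 300 | 0.2% / 0.2% (assumed) | 79.6% |
| 300 | 0.3% / 0.3% | 64.7% |
| 300 | 0.4% / 0.4% | 51.1% |
| 300 | 0.5% / 0.5% (assumed) | 39.5% |
| 300 | 1% / 1% (assumed) | 9.6% |

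The 0.2% row is 1 − (1 − 0.998^300)² = 1 − (1 − 0.5485)² = 0.796. The SAP's safety set stops counting 96 hours after the last dose, so exposure there is shorter and, at the same rates, the chance of an empty arm is if anything higher.

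**The back-up in SAP 6.5.** A ratio of restricted mean time lost is also zero, infinite or undefined when an arm has no events, so it fails in the same trials.

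**What the risk difference gives** (apixaban minus placebo, 300 per arm, percentage points):

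| Events | Estimate | 95% CI | Method |
|---|---|---|---|
| 0 vs 0 | 0.00 | −1.26 to 1.26 | Newcombe |
| 1 vs 0 | 0.33 | −0.96 to 1.86 | Newcombe |
| 2 vs 0 | 0.67 | −0.69 to 2.40 | Newcombe |
| 3 vs 0 | 1.0 | −0.3 to 2.9 | Miettinen-Nurminen |

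Each is finite and two-sided, and shows what excess is excluded.

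**The case against.** A reader might infer that Specific Aim 2 would end without any usable comparison of bleeding. The documents do not support that.

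- The protocol still plans the risk difference with 95% CI for major bleeding, and no SAP text withdraws it. The fault is a mismatch between the two documents.
- Table 6.2.1 requires counts and proportions per arm, from which anyone can compute a risk difference.
- When only one arm is empty (17.8% + 28.4% = about 46% of trials at the proxy rates), the log-rank test still gives a P-value. Only the 12% with both arms empty leave nothing to test.
- It would also be too strong to say that no interval for the hazard ratio exists. The usual Wald interval fails, but a one-sided likelihood bound can be found. For 3 versus 0 bleeds, ignoring small changes in the risk sets, 3 ln[h/(1 + h)] = −1.92 gives a lower limit of about 1.1. The SAP specifies no such bound, and none exists at 0 versus 0.
- SAP 6.4.1 names Cox regression only for the efficacy outcomes. For safety, the estimator and interval method behind the hazard ratio are unstated.

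The rates are also open to challenge. They come from other drugs, in a trial that the protocol describes as having shorter follow-up than planned in some patients. The protocol's Ethical Considerations say the bleeding risk on apixaban in provoked VTE is not yet known. Patients with chronic kidney disease and aspirin users are eligible, so the true rate may be higher. The 58% is therefore conditional, and at 0.5% per arm or above an empty arm is no longer the more likely result.

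One might extend the point to VTE in the subgroups of SAP 6.4.2. With an assumed 20% subgroup (60 per arm) at 1.5%, 0.985^60 = 40% of trials have no apixaban event. That rests on an assumed size, and empty cells are a familiar limit of subgroup analyses, so it adds little.

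What stands: the SAP lists no risk difference, has no zero-event rule, and its conditional back-up fails in the same trials.

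**Conclusion.** The concern holds as a gap between SAP and protocol on a rare primary safety outcome. The SAP leaves the hazard ratio as the only between-arm effect measure for major bleeding. If the cited proxy rates apply with 300 per arm, it is not finite and positive in about 58% of trials; the plausible range runs from about 80% at 0.2% per arm to 10% at 1%. The calculation assumes complete 12-month follow-up and independent binomial counts. In those trials the specified output lacks a finite hazard ratio with a two-sided CI; it does not lack all information on bleeding. The primary efficacy analysis is untouched. Severity: should-fix.

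**What to change.** In SAP 6.4.1 and in the primary safety column of Table 6.2.1:

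1. Add the 12-month risk difference in major bleeding with a 95% score-type CI, naming the method (for example Miettinen-Nurminen or Newcombe).
2. State that this is the measure to interpret when either arm has no events.
3. State that the hazard ratio is reported only when both arms have events.

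This brings the SAP back into line with the protocol. Penalised Cox models, mid-p tests or exact person-time intervals could be added but are not needed to close the gap. The cost is SAP wording and table shells; no new data are required.
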